 - h. Under treatment or expected to taking treatment during the study with medications with a known impact on the cardiac conduction system (e.g., beta blockers, calcium channel blockers, Class Ia or Class III anti-arrhythmic drugs. [amiodarone, bromobenzylamine, sotalol, ibutilide, azimilide, dofetilide]);
 - i. Hypertension (except well-controlled hypertension after pharmacotherapy); systolic

blood pressure < 95 mm Hg or > 140 mm Hg and diastolic blood pressure ≤ 50 mm Hg or ≥ 95 mm Hg at the screening visit;

- j. Resting heart rate < 55 times/min or ventricular rate < 55 times/min in 12-lead ECG at screening visit;
- k. Investigator deems that the 12-lead ECG at screening visit is clinically significant abnormal, such as, myocardial ischemia, any significant cardiac conduction abnormalities (such as the left bundle branch block), that would put the subject at risk or interfere with the study results;
- 1. Any other significant heart disease that the investigator judges would put the subject at risk or interfere with the study results.
- m. Subjects have a family history of premature coronary heart disease.
- 18. History of type 1 diabetes, uncontrolled type 2 diabetes (HbA1c > 7%) judged by investigator, patients with diabetes accompanied with significant complications, e.g., retinopathy or kidney disease.
- 19. The subject has a history of malignancies, including malignant solid tumors and hematological malignancies (Except basal cell carcinomas and in situ squamous carcinomas of the skin that have been excised or cured).
- 20. The subject has had any surgical procedure requiring general anesthesia within 30 days prior to screening or is planning to undergo major surgery during the study period.
- 21. The subject has chronic obstructive pulmonary disease, asthma, pulmonary fibrosis or other any significant history of pulmonary diseases, except for mild intermittent asthma that does not require regular maintenance treatment.
- 22. Pulmonary function test (including examinations of lung ventilation function and pulmonary gas exchange) at the screening visit shows one of the following abnormalities: forced expiratory volume in 1 second (FEV₁) or forced vital capacity (FVC) < 70% of normal expected value.
- 23. During screening period, any of the following laboratory abnormalities:
 - a. Hgb < 8 g/dL;
 - b. WBC count $< 3.5 \times 10^{9}/L$;
 - c. Neutrophils count $< 1.5 \times 10^{9}/L$;
 - d. Lymphocyte count $< 0.8 \times 10^{9}/L$;

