- 15. The subject has any unstable or uncontrolled cardiovascular, pulmonary, hepatic, renal, gastrointestinal, genitourinary, hematological, coagulation, immunological, endocrine/metabolic, or other medical disorders that, in the opinion of the investigator, would confound the study results or compromise subject safety.
- 16. History of uveitis or macular oedema.
- 17. Clinically relevant cardiovascular conditions, including history or presence of any one of below:
 - a. Ischemic heart disease or myocardial infarction; Unstable angina; History of angina pectoris caused by coronary artery spasm or raynaud's phenomenon (Raynauds);
 - b. Congestive heart failure (NYHA class III-IV), cardiac arrest;
 - c. Stroke, transient ischemic attack;
 - d. History of recurrent syncope or positive result of vasovagal syncope tilt test;
 - e. Symptomatic bradycardia, sick sinus syndrome, sinoatrial block, second degree atrioventricular block (e.g., Mobitz type 2 atrioventricular block) or third degree atrioventricular block;
 - f. Congenital long QT syndrome (LQTS) or prolonged QT interval corrected using Fridericia's formula (QTcF) in screening ECG (QTcF >450 ms in men, QTcF > 470 ms in women);
 - g. Subjects at increased risk for QT prolongation due to hypokalemia or hypomagnesemia; or subjects who are currently taking medications to prolong QT interval (e.g., citalopram, chlorpromazine, haloperidol, methadone, and erythromycin) which result in risk for torsades de pointes;
 - h. Under treatment or expected to taking treatment during the study with medications with a known impact on the cardiac conduction system (e.g., beta blockers, calcium channel blockers, Class Ia or Class III anti-arrhythmic drugs [amiodarone, bromobenzylamine, sotalol, ibutilide, azimilide, dofetilide]);
 - i. Hypertension (except well-controlled hypertension after pharmacotherapy); systolic blood pressure < 95 mm Hg or >140 mm Hg and diastolic blood pressure ≤ 50 mm Hg or ≥ 95 mm Hg at the screening visit;
 - j. Resting heart rate < 55 times/min or ventricular rate < 55 times/min in 12-lead ECG at screening visit;
 - k. Investigator deems that the 12-lead ECG at screening visit is clinically significant abnormal, such as myocardial ischemia, any significant cardiac conduction abnormalities (such as the left bundle branch block), that would put the subject at risk or interfere with the study results;

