- 1. Any other significant heart disease that the investigator judges would put the subject at risk or interfere with the study results.
- m. Subjects have a family history of premature coronary heart disease.
- 18. History of type 1 diabetes, uncontrolled type 2 diabetes judged (HbA1c > 7%) by investigator, patients with diabetes accompanied with significant complications, e.g., retinopathy or kidney disease.
- 19. The subject has a history of malignancies, including malignant solid tumors and hematological malignancies (Except basal cell carcinomas and in situ squamous carcinomas of the skin that have been resected or cured).
- 20. The subject has had any surgical procedure requiring general anesthesia within 30 days prior to screening or is planning to undergo major surgery during the study period.
- 21. The subject has chronic obstructive pulmonary disease, asthma, pulmonary fibrosis or any other significant history of pulmonary diseases except for mild intermittent asthma that does not require regular maintenance treatment.
- 22. Pulmonary function test (including examinations of lung ventilation function and pulmonary gas exchange) at the screening visit shows one of the following abnormalities: forced expiratory volume in 1 second (FEV1) or forced vital capacity (FVC) < 70% of normal expected value.
- 23. During screening period, any of the following laboratory abnormalities:
 - a. Hgb < 8 g/dL;
 - b. WBC count $< 3.5 \times 10^{9}/L$;
 - c. Neutrophils count $< 1.5 \times 10^{9}/L$;
 - d. Lymphocyte count $< 0.8 \times 10^{9}/L$;
 - e. Platelet count < 100×10^{9} /L or > 1200×10^{9} /L;
 - f. Serum creatinine $> 124 \mu mol/L$ for female or $> 141 \mu mol/L$ for male;

If the WBC count, neutrophil count or lymphocyte count meets the above criteria during the screening period, a retest can be scheduled during the screening period. It is required that the results of the retest should not meet the above criteria, otherwise subjects do not meet the enrollment criteria.

- 24. Abnormal liver function test during the screening period, such as abnormalities in alanine aminotransferase (ALT), aspartate aminotransferase (AST), γ-glutamyltransferase (γ-GT), alkaline phosphatase (ALK) or serum total bilirubin, which suggest liver disease or liver function impairment. The investigator should make a determination according to the following criteria:

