6.2.1. Cardiac monitoring during titration

In study stage 1, detailed schedule for cardiac monitoring during titration is provided in Table 7.

In the stage 2 sub-study 2, detailed schedule for cardiac monitoring during titration is provided in Table 8.

Table 7. Stage 1 Cardiac monitoring

	Cardiac monitoring											
	Titration day 1				Titration day 2				Titration day 5 and day 8			
Monitoring method	Before administration	Every hour within the 6 h after administration	The 4th hour and 6th hour	Continuous monitoring for 24 hours		Every hour within the 6 h after administration	The 4th hour and 6th hour	Continuous monitoring for 24 hours	administration	within the	6th hour	Continuous monitoring for 24 hours
Vital signs	X	X	X^3		X	X	X^3		X	X	X^3	
12-lead ECG	X		X^3		X		X^3		X		X^3	
Holter monitoring	X ¹			X^2					X^2			X^2

Notes:

- 1. 24-hour Holter monitoring before day 1 will be initiated 1 day before drug administration (baseline day 0).
- 2. 24-hour Holter monitoring will be initiated from 30min ±10min before drug administration until 24 ho urs after drug administration.
- 3. Subjects still need further monitoring in the following cases:
 - at 6 hours after drug administration, the subject's heart rate is still < 45 times/min;
 - at 6 hours after drug administration, the subject's heart rate is still at the lowest level after drug administration;
 - at 6 hours after drug administration, 12-lead ECG shows newly-occurring second degree or higher degree atrioventricular block;
 - at 6 hours after drug administration, the QTcF interval is prolonged (> 450 ms in males; > 470 ms in females);
 - at 6 hours after drug administration, if the subject has symptomatic bradycardia, they will be monitored until it has resolved.

Table 8. Sub-study 2 of Study Stage 2 Cardiac Monitoring

	Cardiac monitoring											
	Titration day 1				Titration day 2				Titration day 5 and day 8			
Monitoring method	Before administration	Every hour within the 6 h after administration	The 4th hour and 6th hour	Continuous monitoring for 24 hours	administration	Every hour within the 6 h after administration	The 4th hour and 6th hour		administration	within the	6th hour	Continuous monitoring for 24 hours
Vital signs	X	X	X^3		X	X	X^3		X	X	X^3	
12-lead ECG	X		X^3		X		X^3		X		X ³	
Holter monitoring	X ¹			X^2					X^2			X^2

Notes:

- 1. 24-hour Holter monitoring before day 1 will be initiated 1 day before drug administration.

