15.5. VITAL SIGNS

The following Vital Signs measurements will be reported for this study:

- Systolic Blood Pressure (SBP) (mmHg)
- Diastolic Blood Pressure (DBP) (mmHg)
- Systolic Blood Pressure(mmHg) (SBP) (Upright Position)
- Diastolic Blood Pressure(mmHg) (DBP) (Upright Position)
- Respiratory Rate (RR) (resp/min)
- Heart Rate (HR) (bpm)
- Temperature (°C)

Document: Statistical Analysis Plan

Author: [name]

Version Number: 1.1

Version Date: 18Jan2023

Template No.: CS_TP_BS016 Revision 5

Reference: CS_WI_BS005

Effective Date: 01Apr2018

- Weight (kg)
- Height (cm)

The following summaries will be provided for vital signs data:

- Actual and change from baseline by visit
- Incidence Markedly Abnormal Values of vital signs:
 - SBP (mmHg) Low is defined as observed value less or equal to 90 and change from baseline less or equal to -20.
 - SBP (mmHg) High is defined as observed value greater or equal to 180 and change from baseline greater or equal to 20.
 - DBP (mmHg) Low is defined as observed value less or equal to 50 and change from baseline less or equal to -15.
 - DBP (mmHg) High is defined as observed value greater or equal to 105 and change from baseline greater or equal to 15.
 - HR (Bpm) Low is defined as observed value less or equal to 50 and change from baseline less or equal to -15.
 - HR (Bpm) High is defined as observed value greater or equal to 120 and change from baseline greater or equal to 15.
 - Temperature (°C) High is defined as observed value greater or equal to 38.3 and change from baseline greater or equal to 1.1.
 - Weight (kg) Low is defined as percentage change from baseline less or equal to -7.0%.
 - Weight (kg) High is defined as percentage change from baseline greater or equal to 7.0%.
- Listing of vital signs

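### Exclusion 17i joins the systolic and diastolic limits with an unbracketed *and*: 120/48 escapes the numeric exclusion on either logical parse, and 90/60 escapes it or not depending on the parse

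*Protocol*

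**What the plan says.** Exclusion 17 in Protocol 5.4.1 lists cardiovascular conditions, and any one lettered item excludes. Item 17i has two parts separated by a semicolon. The first is hypertension, with an exception for hypertension well controlled on drugs. The second is numeric: "systolic blood pressure < 95 mm Hg or >140 mm Hg and diastolic blood pressure ≤ 50 mm Hg or ≥ 95 mm Hg", measured at the screening visit. The Synopsis has the same limits and the same conjunction: "blood pressure < 95 mm Hg or > 140 mm Hg and diastolic blood pressure ≤ 50 mm Hg or ≥ 95 mm Hg".

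The lead-in governs how the lettered items combine. It does not say how the two pressures inside 17i combine, and nothing else in the protocol or SAP says that one pressure alone is enough.

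Nearby criteria use *or* where a single value excludes. Item 17j reads "Resting heart rate < 55 times/min or ventricular rate < 55 times/min in 12-lead ECG", and exclusion 22 reads "forced expiratory volume in 1 second (FEV1) or forced vital capacity (FVC) < 70% of normal expected value". SAP 15.5 flags low pressures on study separately: "SBP (mmHg) Low is defined as observed value less or equal to 90" and "DBP (mmHg) Low is defined as observed value less or equal to 50", each together with a fall from baseline.

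**The concern.** An eligibility threshold should give the same answer whoever reads it. Here the same screening reading can be eligible at one site and ineligible at another, across about 77 sites in four countries. The sponsor set lower limits for both pressures for a drug that slows the heart after the first doses. If *and* is taken at its word, those lower limits do not act on an isolated low pressure.

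Two things are at stake. One is the sponsor's own entry safeguard. The other is the per-protocol set: SAP 5.1 removes major eligibility deviations from the PPS, and SAP 14.2.2 names the PPS among the sets for the primary efficacy analysis. Whether a 120/48 entry is a deviation at all turns on one word.

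**Working it through.** The plan gives no figure to reproduce on this point. The check is a logical evaluation of 17i.

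Inputs, from Protocol 5.4.1 item 17i (S = systolic, D = diastolic, whole mm Hg):

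- systolic out of range: S < 95 or S > 140
- diastolic out of range: D ≤ 50 or D ≥ 95

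Three readings of the sentence:

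- **Grouped:** (S < 95 or S > 140) and (D ≤ 50 or D ≥ 95). This is the natural reading of the words.
- **Operator precedence** (*and* binds before *or*): S < 95, or (S > 140 and D ≤ 50), or D ≥ 95.
- **Either:** S < 95 or S > 140 or D ≤ 50 or D ≥ 95.

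| Reading | Grouped | Precedence | Either |
|---|---|---|---|
| 120/48 | not excluded | not excluded | excluded |
| 90/60 | not excluded | excluded | excluded |
| 150/80 | not excluded | not excluded | excluded |
| 130/97 | not excluded | excluded | excluded |
| 90/48 | excluded | excluded | excluded |
| 150/98 | excluded | excluded | excluded |
| 120/75 | not excluded | not excluded | not excluded |

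In general, the grouped rule misses four regions:

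- S < 95 with D 51–94
- D ≤ 50 with S 95–140
- S > 140 with D 51–94
- D ≥ 95 with S 95–140

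The precedence rule still misses the second and third. The two high-pressure regions may be caught by the hypertension clause in the first half of 17i. That clause offers nothing for low pressure.

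**What was meant.** The grouped rule has four combinations, and one of them, S < 95 with D ≥ 95, would put diastolic above systolic, which is impossible. A deliberate joint rule would not contain it. Each pressure also has its own two-sided limits, and 17j and exclusion 22 use *or*. SAP 15.5 treats each low pressure as abnormal in its own right and shares the diastolic cut-off of 50. That is supporting evidence only: its systolic cut-off is 90 rather than 95, it also needs a fall from baseline, and it is not an eligibility rule.

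**What else could stop entry.** Exclusion 17d covers recurrent syncope or a positive tilt test and needs no investigator opinion, but it would not catch a symptomless low reading. Exclusion 15 covers unstable or uncontrolled disorders that, "in the opinion of the investigator, would confound the study results or compromise subject safety". No other blood pressure value decides entry.

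**What happens after dosing.** Table 2 note 7 has vital signs taken before dosing and hourly for 6 hours on days 1, 2, 5 and 8. Protocol 7.3.2 requires clinically significant changes to be confirmed by repeat measurement; its orthostatic check leads to documentation. Protocol 7.5 allows more frequent assessment when clinically indicated, and its bradycardia guidance gives atropine for symptoms or hypotension, then dopamine or epinephrine if heart rate or pressure does not respond. Table 7 note 3 introduces its list with "Subjects still need further monitoring in the following cases"; the five triggers are heart rate below 45, heart rate still at its lowest, new AV block, long QTcF and symptomatic bradycardia. None is a blood pressure value.

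**Effect on the analysis.** FAS and mFAS membership (SAP 5.1) depends on randomization, dosing and, for mFAS, week-12 scores missing because of COVID-19. The sample-size inputs (SAP 7.4) are the score difference, its standard deviation, alpha, power and dropout. None involves 17i.

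**The case against.** The strongest reply is that this is loose drafting that most investigators will read as intended. A clinician may take *and* as listing two sets of abnormal values, each enough to exclude. That is plausible, and it agrees with the likely intent. It does not settle the matter, because nothing in the text says so and two other parses are open.

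Several stronger inferences are tempting, and the documents do not support them:

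- **That 90/60 is eligible on any literal reading.** It is excluded under strict operator precedence. Only 120/48 escapes on both logical parses.
- **That only investigator judgement remains for low pressure.** Exclusion 17d is a non-discretionary, though partial, backstop.
- **That low pressure goes unmanaged during dosing.** Protocol 7.5 covers its treatment, and Protocol 5.4.4 allows termination for an adverse event that poses unacceptable risk. What is missing is a numeric blood pressure trigger.
- **That CBP-307 lowers blood pressure.** Protocol 3.4.4 and 3.5 report no apparent effect, and the dog finding in 3.3.1 was a slight diastolic rise. The phase I evidence is limited to healthy subjects, with six on active drug per cohort.
- **That such patients were enrolled.** The wording is not evidence of that.

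The analogies with 17j and exclusion 22 are also imperfect, since each joins one-sided limits. They show drafting habit, not proof of intent.

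**Conclusion.** The wording of 17i is defective in both places. An isolated low diastolic (D ≤ 50 with S 95–140) does not meet the numeric exclusion on either logical parse. An isolated low systolic (S < 95 with D 51–94) does not meet it on the natural grouped parse. Isolated high readings miss it on the grouped parse and rest on the hypertension clause. Exclusion on either pressure alone was almost certainly intended.

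The size is small. The safety effect is limited by the partial backstops, the post-dose monitoring and the absence of a reported hypotensive effect. FAS, mFAS, alpha and power are unaffected. The PPS changes only if an entry of this kind occurred and is classed as a major eligibility deviation. How many patients this concerns cannot be said, because the documents give no frequency. This is a worthwhile wording correction, not a threat to the primary result. The conclusion assumes that no site instruction or eCRF check outside these documents already fixes the reading.

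**What to change.** In Protocol 5.4.1 and the Synopsis, replace the numeric part of 17i with: *systolic < 95 or > 140 mm Hg, or diastolic ≤ 50 or ≥ 95 mm Hg at the screening visit (either one excludes)*. State that these limits also define well-controlled for treated hypertension; otherwise a treated patient at 142/80 meets the numeric limit and may also claim the exception. Apply the same reading in the eCRF eligibility check, whose current logic is not in these documents and should be confirmed, and in the PPS deviation classification.

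The cost is one edit in two places, a check of the eCRF logic, and an amendment that needs IEC/IRB approval under Protocol 2.1. The downside is some additional screen failures, in a number the documents do not give. The Synopsis plans study completion in September 2022 and the SAP is dated January 2023, so screening has probably closed. In that case, what remains is to record one reading of 17i for the PPS, preferably before treatment codes are opened, and to use the corrected wording if the criterion is reused.

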5.4.3. Re-screening after the failure of screening

The numbers of all subjects who fail the screening will not be used again. Whether a subject who fails the screening is allowed to undergo re-screening will be evaluated by the sponsor's medical monitor based on individual case. Subjects receiving re-screening will be required to complete all laboratory tests and procedures during the screening period, including colonoscopy (except that recent colonoscopy videos are available for the centralized reading at the site and the ilecolonoscopy is performed within 30 days prior to the first dose). In case the results of the pulmonary function test, ophthalmologic examination (including OCT) or dermatology examination during initial screening period at the study site are within 30 days

prior to the first dose, the results could be re-used after the investigators' evaluation based on individual case. Subject is allowed to be re-screened only once.

5.4.4. Criteria for termination of treatment or early withdrawal of subjects

Subjects should be encouraged to complete the study, but they are allowed to voluntarily withdraw from the study at any time during its conduct. The investigator should provide written statements of the withdrawal of subjects from the study. Primary reasons why subjects terminate or withdraw from the study or discontinue the investigational product should be recorded in the eCRF according to the following classifications.

1) Adverse events (AEs)

The Subject has experienced an AE that requires early termination because continued participation imposes an unacceptable risk to the subject's health or the subject is unwilling to continue because of the AE.

• Liver function test (LFT) abnormalities

The investigational product should be discontinued immediately, and appropriate clinical follow-up should be performed (including repeated laboratory tests until the subject's laboratory measurements returns to normal or baseline, please refer to Section 7.5), if the following circumstances occur at any time during study medication treatment:

- ALT or AST $> 8 \times ULN$, or
- ALT or AST > 5 \times ULN and a re test > 5 \times ULN, or
- ALT or AST > 3 \times ULN and elevated total bilirubin > 2 \times ULN, or international normalized ratio (INR) > 1.5, or
- ALT or AST > 3 ×ULN with fatigue, nausea, vomiting, right upper quadrant pain or tenderness, fever and rashes.

• Decrease in pulmonary function

If the subject's pulmonary function test results (FEV₁ and/or FVC) fall below 50% of the predicted values, treatment should be discontinued immediately, and appropriate clinical follow-up should be performed (please refer to Section 7.5).

Macular edema

All subjects diagnosed with macular edema must discontinue the investigational product (see Section 7.5).

2) Significant protocol deviation at the time of enrollment or during the study

The discovery post randomization that the subject fails to meet protocol entry criteria or does not adhere to protocol requirements, and continued participation in the study may poses unacceptable risk to the subject's health.

3) Lost to follow-up

The subject does not return to the study site, and the investigator makes multiple attempts to contact the subject but fails. If a subject is lost to follow-up, the investigator should make every effort to contact the subject and record each attempt to contact the subject (where possible, 3 telephone calls and, if necessary, a certified letter to the subject's last known mailing address or local equivalent methods).

4) Subject non-compliance with the protocol

If a subject is in significant non-compliance with the protocol, the subject could be early terminated after discussion/consultation by the investigator, the medical monitor of the contract research organization (CRO), and sponsor.

5) Withdrawal of informed consent by the subject

The subject voluntary withdraws from the study. The subject (or their legal representatives) wishes to withdraw from the study. The reason for withdrawal, if provided should be recorded in the eCRF.

6) Termination of study

Sponsor, Ethics Committee or regulatory body terminates the study.

7) Pregnancy

Subject pregnancy.

Note: If a subject is found to be pregnant, the subject must withdraw from the study immediately. The procedure for withdrawal from the study is detailed in Section 8.8.

8) Treatment failure or disease progression

Study stage 1: The investigator considers that subject is not benefiting from investigational treatment, and present with disease progression during the study: e.g., in the opinion of the investigator, continued participation would pose an unacceptable risk to the subject or need for surgical intervention for treatment of UC.

Study stage 2: In sub-study 1, if the subject present with UC recurrence during maintenance treatment, the subject is required to terminate the treatment and withdraw from the study.

UC disease recurrence i.e., an increased activity of UC, is defined as a repeated (occurring at 2 consecutive visits) partial Mayo score that is at least 5 points and is also \geq 3 points higher than the score at week 12 (the end of induction therapy), and where the possibility of increased

disease activity being due to other potential factors unrelated to UC can be excluded (e.g., infection, medication changes).

In sub-study 2, if subjects have not achieved clinical response yet at week 24, they will be required to terminate treatment and withdraw from the study. In addition, for all subjects who enter the study stage 2, if the investigator judges that they are not benefiting from the study treatment, or present with disease progression during the study period, or need for surgical intervention for UC treatment, the investigational treatment should also be terminated.

9) Others

Note: Specific reasons should be recorded in the eCRF. The investigator should do their utmost to determine the primary reason of withdrawal, and if possible, document it (e.g., withdrawal due to AEs or treatment failure).

5.4.5. Criteria for termination of the clinical study.

The study may be terminated prematurely in case of the following:

- The principal investigator and sponsor believe that the number and severity of AEs indicate that the study must be terminated.
- Newly obtained data raise concerns about the safety of the investigational product: continuation of the study may pose a risk to subjects.
- The principal investigator and sponsor believe that a flawed study design or unplanned unblinding has impaired the integrity of the study, thereby making it impossible to evaluate the efficacy and safety of the investigational product.

The premature termination of the study must be determined and recorded by the principal investigator in consultation with sponsor. Study results must be reported as far as possible according to the protocol requirements.

